The expected	The screening period from signing the informed consent form to enrollment is expected to be 4 weeks, the treatment period is 1~8 weeks, and the short-term follow up after the last treatment are divided into
the	short-term follow-up and long-term follow-up, and the maximum duration
unc narticinant's	of expected participation of each subject from screening to the end of short-term
participation	follow-up is 12 weeks +3 months. Long-term follow-up continued after the end of the
participation	short-term follow-up until the fifth year after the end of the last radiotherapy.
Expected	The first subject is expected to be enrolled in December 2021, and the clinical trial
overall	institution expects to enroll 8-18 subjects per month, for a total enrollment time of
duration of	about 4 months, and the last 1 subject ends the trial (short-term follow-up) is End In
clinical trials	September 2022, the overall duration of the clinical trial included all working
and long-term	hours before, during and after the start of all clinical trials, and the overall duration of
follow-up	the clinical trial was 16 months.

Protocol summary

	The first subject is expected to start long-term follow-up in May 2022 and the last		
	one subject to end long-term follow-up in June 2027, and the overall duration		
	of long-term follow-up in clinical trials includes all clinical runs, After all working		
	hours ended, the total long-term follow-up period for clinical studies was		
	approximately 62 months.		
	Disease Control Rate (DCR).		
	Evaluation time: 3 months ± 7 days after the last treatment.		
	Definition of indicators: Complete Response (CR), Partial Response (PR), Stable		
	Disease (SD) for disease control; No biochemical recurrence at the end of prostate		
D .	cancer treatment, no regional lymph nodes or distant metastases, considered disease		
Primary	control. Proportion of participants who developed disease control three months after		
effectiveness	the end of the last radiotherapy. Participants who discontinued the trial for any reason		
Evaluation	(except loss to follow-up) before the end of radiation therapy were considered to have		
indicators	progression (PD) or uncontrolled.		
	Evaluation methodology: Response Evaluation Criteria in Solid Tumors RECIST		
	Version 1.1 (RECIST 1.1) by an independent imaging review team Changes in		
	tumour CT or MRI imaging before and after treatment were assessed. At 3 months		

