3.1.4 Effectiveness evaluation methods

If it is not possible to follow up at the clinical trial center according to the visit arrangement due to the epidemic, the clinical examination can be examined by other tertiary hospitals, and the test results will be transmitted back to the clinical trial center for evaluation; The carrier of imaging data in the outer hospital is not limited, and it is necessary to ensure that the imaging department of the center can be opened and read.

3.1.4.1 The main effectiveness evaluation indicators and the methods and time selection of their evaluation, recording and analysis

(1) Tumor disease control rate (DCR).

Reason for selection: According to the clinical trial effectiveness evaluation in the "Guidelines for the Review of Clinical Evaluation Technologies of Proton Carbon Ion Therapy System" (CFDA Circular No. 4 [2018]): "In view of the local characteristics of radiotherapy, it is recommended that the efficacy evaluation should be based on local control, and according to the different diseases, the common standards in clinical research, such as the efficacy evaluation criteria for solid tumors, should be reasonably adopted RECIST. The efficacy evaluation can be divided into complete response CR, partial response PR, disease stable SD, disease progression PD, and the effective definition is: "CR+PR+SD." "; Due to the particularity of the disease, the evaluation method recommended in the relevant diagnosis and treatment guidelines is selected. The tumor disease

control rate was selected as the main effectiveness evaluation index, which was relatively objective and reproducible, and adopted the common standard in clinical research, which was widely recognized and applied by clinicians.

Definition of indicators: the occurrence of CR, PR and SD after the end of treatment is disease control; No biochemical recurrence at the end of prostate cancer treatment, no regional lymph nodes or distant metastases, considered disease control. Proportion of participants who developed disease control three months after the end of the last radiotherapy.

Metric type: Qualitative.

Data collection time: screening period, 3 months \pm 7 days after the end of the last treatment.

Evaluation time: 3 months \pm 7 days after the end of the last treatment.

Site of evaluation: Tumor receiving radiation therapy.

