Evaluation method: The changes in tumor CT or MRI imaging before and after treatment were evaluated by an independent imaging review panel according to RECIST 1.1. At 3 months of radiographic evaluation, if PD is found, PET-CT is required to confirm it.

Calculation formula: DCR = number of disease control subjects / total number of subjects × 100%.

Criteria: See RECIST 1.1 for details. At the time of 3-month imaging evaluation, if the patient is found to have PD, PET-CT examination is required to confirm it, if progress is confirmed, it is recorded as PD, if progress cannot be confirmed, it may be false progression, and it is recorded as SD. If prostate cancer does not have biochemical recurrence, PET-CT examination is not required, and there is no metastasis by default, which is regarded as tumor control, and if biochemical recurrence occurs, it is regarded as tumor not controlled, and PET-CT is required to confirm tumor metastasis.

Note: Participants who aborted the trial for any reason (except loss to follow-up) before the end of the last radiation therapy were considered to have disease progression (PD) or were not controlled. Disease site evaluation uses the same approach as baseline, including consistent contrasted/non-contrast scans and prompt scanning. If changes are needed, the case must be discussed with a radiologist to determine whether an alternative approach is possible. If not, the objective situation in the future is unclear.

3.1.4.2 Secondary effectiveness evaluation indicators and their methods and timing of evaluation, recording, analysis

(1) Objective response rate (ORR).

Reason for selection: The Guidelines for the Review of Clinical Evaluation Technologies of Proton Carbon Ion Therapy Systems (CFDA Circular No. 4 [2018]) recommends the use of the latest version of the commonly used evaluation criteria for radiation oncology as the clinical trial evaluation criteria, so RECIST 1.1 is used Relevant indicators as effectiveness evaluation criteria; Due to the particularity of the disease, the evaluation method recommended in the relevant diagnosis and treatment guidelines is selected. All of them can directly measure the effect of radiotherapy and are widely recognized and applied by clinicians.

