4.4 Expected shedding rate

In the sample size estimation process, the expected shedding rate is 10%.

This dropout rate refers to the proportion of participants who ultimately could not be included in the primary analysis. Shedding subjects are subjects who have been identified by the investigator as having serious protocol deviations. May include, but is not limited to, the following: the subject violates the inclusion criteria; Participants were not treated with experimental devices; Participants used concomitant medications/devices that are prohibited by the protocol; lack of data on key evaluation indicators; Participants did not obtain any data, etc.

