- (3) The missing values of DCR and primary safety evaluation indicators
 (proportion of CTCAE grade 3 toxicities, proportion of CTCAE grade
 4 and 5 toxicities) at 3 months after the end of treatment can be estimated using worst-case scenarios.
- (4) The missing values of qualitative secondary effectiveness evaluation indicators ORR, DCR and long-term follow-up effectiveness evaluation indicators can be estimated using worst-case scenarios;
- (5) The missing values of quantitative secondary efficacy evaluation indicators DOR, tumor markers, product ease assessment and long-term follow-up effectiveness evaluation indicators were not estimated.
- (6) Erroneous, unreasonable data (out-of-range data and data that contradicts other data or indicators of the study protocol) can be treated as missing values;
- (7) Worst-case estimates are used for missing values for all minor safety indicators;

- (8) The sensitivity analysis of the main effectiveness evaluation indicators and main safety evaluation indicators after treatment was carried out in the whole analysis center.
- (9) The sensitivity analysis of all secondary effectiveness evaluation indicators after treatment was carried out in the whole analysis center.
- (10) For all secondary safety evaluation indicators after treatment, sensitivity analysis was carried out in the security dataset.

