4.9 Selection criteria and rationale for participants included in the analysis

Full Analysis Set (FAS): All subjects who received at least 1 investigational device treatment and at least one post-baseline observation data will be enrolled in FAS, according to the basic principles of intention-to-heart analysis. FAS will be used as the primary population for baseline data and sensitivity analysis for validity evaluation. Participants may only be excluded in very limited circumstances, including when important inclusion criteria are violated and no observational data are available after enrollment.

Compliant protocol set (PPS): is a subset of FAS, defined as subjects who have measurable lesions at baseline and have completed at least one assessment of primary efficacy indicators after baseline. PPS will be the primary population for the effectiveness evaluation of this study.

Safety dataset (SS): all participants who received at least 1 study device treatment and at least one safety assessment. SS will be the primary population for safety analysis in this study.

The assessment of baseline characteristics will use the full set of analyses; The evaluation of effectiveness will use both the full analysis set and the conforming protocol set; Security analysis uses security datasets.

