ECOG	Eastern Cooperative Oncology Group	Eastern Oncology Collaborative Group
FAS	Full Analysis Set	Full analysis set
ICH	The International Council for Harmonisation of Technical Requirement for Pharmaceuticals for Human Use	International Harmonization Council for Technical Requirements for Pharmaceuticals for Human Use
MedDRA	Medical Dictionary for Regulatory Activities	Medical Dictionary of Regulatory Activities
NYHA	New York Heart Association	New York Heart Society
OIS	Oncology Information System	Oncology Information System
ORR	Objective Response Rate	Objective response rate
PD	Progressive Disease	Disease progression
PET	Positron Emission Tomography	Positron emission tomography
PN	Preferred Name	Preferred name
PPS	Per-Protocol Set	Conforms to the scenario set
PR	Partial Response	Partial relief
PSA	Prostate Specific Antigen	Prostate-specific antigens
PT	Preferred Terms	Preferred term
SAE	Serious Adverse Events	Serious adverse events
SAP	Statistical Analysis Plan	Statistical analysis plan
SAS	Statistical Analysis System	Statistical analysis system
SD	Stable Disease	Stable disease
SLD	Sum of Longest Diameter	Sum of longest diameters of tumors
SOC	System Organ Class	Systematic organ classification
SS	Safety Set	Security datasets
TEAE	Treatment Emergent Adverse Event	Adverse events during the treatment period
TNM	Tumor, Node, Metastasis	Tumors, lymph nodes, metastases
WHODD	World Health Organization Drug Dictionary	World Health Organization Dictionary of Medicines

Page 1 / 17 Confidential Information

WOCF Worst Observation Carried Forward Worst observed data carryover

Confidential Information Page 2 / 17

Statistical Analysis Plan Version: V1.0

Date: 2022-11-11

This statistical analysis plan (SAP) refers to the E9 guiding principles of the International Council for

Harmonization of Technical Requirements for Pharmaceuticals for Human Use (ICH) Guidance for Industry:

Statistical Principles for Clinical Trials ICH E3 Guidance for Industry: Structure and Content of Clinical Study

Reports Relevant national regulations and guidelines, according to the clinical study protocol titled "Varian

ProBeam Proton Therapy System China Clinical Trial (Hefei)" (version number: V1.4, Version Date: 2022-06-

10) developed.

This SAP describes the rules for the presentation and analysis of short-term follow-up efficacy data and

safety evaluation data specified in the protocol, and describes in detail the data, variables and statistical methods

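### Subjects who leave during radiotherapy are failures by definition, yet the deciding per-protocol set may exclude them, and neither document says which applies

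*Protocol*

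**What the plan says.** **Endpoint.** The note to the primary disease control rate (DCR) in Protocol 3.1.4.1 sets the rule for early leavers: those that "aborted the trial for any reason (except loss to follow-up) before the end of the last radiation therapy were considered to have disease progression", or else not to be controlled. The protocol summary has the same rule.

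**Timing.** For the primary DCR, Protocol 3.1.4.1 gives "Data collection time: screening period, 3 months" after the last treatment. The secondary DCR adds a 1-month assessment. No efficacy imaging is planned during radiotherapy.

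**Analysis set.** Protocol 4.9 limits the PPS to FAS subjects with measurable baseline lesions who have "completed at least one assessment of primary efficacy indicators after baseline. PPS will be the primary population for the effectiveness evaluation of this study". SAP 3 repeats this. SAP 5.6 lets the PPS prevail if it and the FAS disagree. SAP 5.3.2 leaves set membership to a data review meeting before lock.

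**Dropout.** Protocol 4.4 says: "This dropout rate refers to the proportion of participants who ultimately could not be included in the primary analysis". Its list of possible reasons includes "lack of data on key evaluation indicators".

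**Missing values.** Protocol 4.7.2 says that missing DCR values "at 3 months after the end of treatment can be estimated using worst-case scenarios", without naming the set. SAP 4.3 says that filling need not be considered in the PPS and that missing primary values in the FAS are not filled. SAP 5.4.1 fills them in the FAS by worst observation carried forward (WOCF), and SAP 4.1 and 5.6 presuppose the same.

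**SAP endpoint.** SAP 2.1.1 and 5.4.1 do not repeat the early-leaver rule, although the SAP introduction says that it was developed "according to the clinical study protocol titled" for this trial, in version 1.4.

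**The concern.** The endpoint rule assigns a failure to exactly those subjects who are least likely to have a post-baseline scan. The PPS definition asks for a completed assessment. If an assigned progression counts as one, the two texts fit together and nothing is lost. If it does not, the rule has no effect in the set that decides the trial, and the observed DCR rises against the fixed 80% target.

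The FAS is not a dependable safeguard. The SAP contradicts itself on whether its missing primary values are filled. WOCF has nothing post-baseline to carry for a subject never scanned. SAP 4.1 also admits unscheduled data, so unless the progression rule is applied first, a withdrawal scan read as stable disease would be carried as controlled where the protocol assigns progression.

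The choice of reading would fall to the data review meeting, in a single-arm trial where nothing masks outcomes by treatment.

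**Working it through.** **Inputs.** Target 80%, two-sided alpha 0.05, power 80%, at least 42 evaluable and 47 enrolled (Protocol 4.2, 4.3); expected value 95% (Protocol 3.1.2); dropout 10% (Protocol 4.4); pass if the lower 95% limit exceeds 80% (Protocol 4.5); Clopper-Pearson interval (Protocol 4.7.1). The rates of early leaving and of loss to follow-up are assumptions. All subjects are taken to be treated and to have measurable lesions.

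**The plan's own figure.** n = [(1.960 × √(0.80 × 0.20) + 0.842 × √(0.95 × 0.05)) / 0.15]² = 41.6, rounded up to 42; 42 / 0.9 = 46.7, rounded up to 47. Both figures reproduce, so the sample size is not at issue.

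**Failures allowed.** The least number controlled, k(n), that gives an exact lower limit above 80%:

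| n | k(n) | Failures allowed | Lower limit at k(n) |
|---|---|---|---|
| 47 | 44 | 3 | 82.5% |
| 46 | 43 | 3 | 82.1% |
| 45 | 42 | 3 | 81.7% |
| 44 | 41 | 3 | 81.3% |
| 43 | 40 | 3 | 80.9% |
| 42 | 39 | 3 | 80.5% |

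The allowance does not shrink as subjects are removed, so each excluded leaver is one failure not counted.

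**One subject.** With one leaver and three other failures, exclusion gives 43/46, lower limit 82.1% (pass). Counting the leaver gives 43/47, lower limit 79.6% (fail).

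**How often the readings disagree.** With exactly m leavers and 95% control in the other 47 − m, the chance of opposite verdicts is P(X ≥ k(47 − m)) − P(X ≥ 44), X ~ Bin(47 − m, 0.95):
- m = 1: 80.3% − 59.4% = 20.9%
- m = 2: 81.3% − 33.5% = 47.8%

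**False pass under exclusion.** Let the true DCR, with leavers as failures, be exactly 80%, and let a proportion d be excluded. Then n ~ Bin(47, 1 − d), and the control rate among those kept is 0.80 / (1 − d). Summing P(X ≥ k(n)) over n:

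| d | 0% | 1% | 2% | 3% | 5% |
|---|---|---|---|---|---|
| Chance of passing | 0.9% | 1.4% | 2.1% | 3.1% | 6.3% |

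It crosses the one-sided 2.5% level at d = 2.46%, which is 0.0246 × 47 = 1.2 subjects expected.

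**WOCF route in the FAS.** Take 43 other subjects controlled, three other failures and one leaver with an unscheduled scan read as stable disease. WOCF gives 44/47 (82.5%, pass); the protocol's rule gives 43/47 (79.6%, fail).

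**The case against.** The strongest reply is that the protocol already answers the question. The rule is part of the endpoint, so a leaver's value is assigned and not missing. A reading that removes these subjects from the PPS would make the rule idle in the set the protocol calls primary. The SAP says it follows version 1.4, and its section on changes does not drop the rule. That is a fair reading and may be the intended one. It is not written down, however, and the word completed, the SAP's remark on filling in the PPS and the protocol's dropout definition all lean the other way.

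Other points stand in part:
- Protocol 4.4 ties dropout to serious deviations identified by the investigator and offers its list only as possibilities, so it is soft support.
- Protocol 4.5 names no analysis set, and SAP 5.4.1 uses both. That the PPS decides rests on Protocol 4.9, SAP 3 and SAP 5.6. SAP 5.6 also asks for differences to be discussed, so a reversal would be visible.
- A leaver with an unscheduled scan might qualify for the PPS anyway.
- At 1% or 2% excluded, the false-pass chance stays below 2.5%.
- If the PPS falls to between 34 and 40 subjects, for example through the measurable-lesion condition, only 2 failures are allowed.
- The conflict between SAP 4.3 and 5.4.1 affects all missing FAS values, not only these, and settling it does not settle the PPS question.

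None of this supplies the missing rule.

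**Conclusion.** The concern holds, as something that should be fixed, with medium confidence. The plan does not say whether protocol-defined failures stay in the deciding denominator, and its fallback set has contradictory instructions. The harm arises under one reading only, and only for subjects who leave during radiotherapy, are not lost to follow-up and have no post-baseline assessment. The documents give no rate for this group; the planned 10% dropout covers other causes too.

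Within those limits the effect can decide the trial. A single exclusion can turn a fail into a pass, and one-sided error control at 2.5% is lost once slightly more than one subject in 47 is expected to be excluded.

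**What to change.** 1. Restate the rule on progression or non-control in SAP 2.1.1 and 5.4.1, applied before any WOCF. State in Protocol 4.9 and SAP 3 that an assigned progression counts as a completed primary efficacy assessment, and in Protocol 4.4 that it is not missing data. These subjects then stay in both denominators as failures.
2. Reconcile SAP 4.3 with SAP 5.4.1 so that the FAS sensitivity analysis uses the worst-case handling that Protocol 4.7.2 permits, with a missing 3-month DCR counted as not controlled. Say that this also counts losses to follow-up as failures, in that analysis only.

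PPS primacy and the SAP 5.6 tie-break stay as they are. Letting the FAS decide, with the rule applied, is another route but a larger change.

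**Cost.** Wording only, with no new data, but some chance of passing is given up. Take 95% control in completers, a proportion d leaving early and l lost to follow-up. With leavers counted and l = 0, the chance of passing is P(X ≥ 44), X ~ Bin(47, 0.95(1 − d)). With leavers excluded, P(X ≥ k(n)) at 0.95 is summed over n ~ Bin(47, 1 − d).

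| d (l = 0) | Leavers counted | Leavers excluded |
|---|---|---|
| 0% | 79.3% | 79.3% |
| 2% | 59.1% | 80.2% |
| 5% | 31.5% | 81.5% |

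The second change leaves the PPS verdict alone but makes the FAS stricter. The FAS chance is P(X ≥ 44), X ~ Bin(47, 0.95(1 − d − l)). The PPS has n ~ Bin(47, 1 − l) and control rate 0.95(1 − d − l)/(1 − l).

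| d | l | FAS | PPS after change 1 |
|---|---|---|---|
| 0% | 2% | 59.1% | 80.2% |
| 0% | 5% | 31.5% | 81.5% |
| 2% | 3% | 31.5% | 60.7% |

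The two sets will disagree more often, and SAP 5.6 will still decide by the PPS. All values of d and l are assumptions.

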4.10 Covariate and subgroup analysis

Subgroup analysis as necessary was not precluded. Subgroups include, but are not limited to:

 Tumor sites (tumors of the nervous system, head and neck, chest, abdomen, spine, pelvis, extremities, etc.).

ECOG	Eastern Cooperative Oncology Group	Eastern Oncology Collaborative Group
FAS	Full Analysis Set	Full analysis set
ICH	The International Council for Harmonisation of Technical Requirement for Pharmaceuticals for Human Use	International Harmonization Council for Technical Requirements for Pharmaceuticals for Human Use
MedDRA	Medical Dictionary for Regulatory Activities	Medical Dictionary of Regulatory Activities
NYHA	New York Heart Association	New York Heart Society
OIS	Oncology Information System	Oncology Information System
ORR	Objective Response Rate	Objective response rate
PD	Progressive Disease	Disease progression
PET	Positron Emission Tomography	Positron emission tomography
PN	Preferred Name	Preferred name
PPS	Per-Protocol Set	Conforms to the scenario set
PR	Partial Response	Partial relief
PSA	Prostate Specific Antigen	Prostate-specific antigens
PT	Preferred Terms	Preferred term
SAE	Serious Adverse Events	Serious adverse events
SAP	Statistical Analysis Plan	Statistical analysis plan
SAS	Statistical Analysis System	Statistical analysis system
SD	Stable Disease	Stable disease
SLD	Sum of Longest Diameter	Sum of longest diameters of tumors
SOC	System Organ Class	Systematic organ classification
SS	Safety Set	Security datasets
TEAE	Treatment Emergent Adverse Event	Adverse events during the treatment period
TNM	Tumor, Node, Metastasis	Tumors, lymph nodes, metastases
WHODD	World Health Organization Drug Dictionary	World Health Organization Dictionary of Medicines

Page 1 / 17 Confidential Information

WOCF Worst Observation Carried Forward Worst observed data carryover

Confidential Information Page 2 / 17

Statistical Analysis Plan Version: V1.0

Date: 2022-11-11

This statistical analysis plan (SAP) refers to the E9 guiding principles of the International Council for

Harmonization of Technical Requirements for Pharmaceuticals for Human Use (ICH) Guidance for Industry:

Statistical Principles for Clinical Trials ICH E3 Guidance for Industry: Structure and Content of Clinical Study

Reports Relevant national regulations and guidelines, according to the clinical study protocol titled "Varian

ProBeam Proton Therapy System China Clinical Trial (Hefei)" (version number: V1.4, Version Date: 2022-06-

10) developed.

This SAP describes the rules for the presentation and analysis of short-term follow-up efficacy data and

safety evaluation data specified in the protocol, and describes in detail the data, variables and statistical methods

that need to be summarized and analyzed. Unless otherwise specified, the final analysis of short-term follow-up

will be performed in accordance with this plan, and the presentation of statistical analysis results may be fine-

tuned to some extent during the statistical analysis phase.

This SAP was established and finalized prior to the locking of this clinical trial database.

1 Overview of the trial

1.1 **Objective**

